14.6. Secondary Analysis

N/A.

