Study Responsible Clinician	<hr/> 
See Electronic Signature Report [name], OD Principal Research Optometrist
	<hr/> 
DATE

Clinical Operations Manager	<hr/> 
See Electronic Signature Report [REDACTED] Clinical Operations Department
	<hr/> 
DATE

Biostatistician	<hr/> 
See Electronic Signature Report [REDACTED] Biostatistician II, Clinical Sciences
	<hr/> 
DATE

Biostatistics Reviewer	<hr/> 
See Electronic Signature Report [REDACTED]. Senior Manager of Biostatistics, Clinical Sciences
	<hr/> 
DATE

Data Management	<hr/> 
See Electronic Signature Report [REDACTED] Clinical Project Manager – Data & Systems, Clinical Operations
	<hr/> 
DATE

Approver:	<hr/> 
See Electronic Signature Report [REDACTED] Director of Global Medical Affairs
	<hr/> 
DATE

CHANGE HISTORY

Version	Originator	Description of Change(s) and Section Number(s) Affected	Date
1.0	[name] & [name]	Original Protocol	01 OCT 2018
2.0	[name]	
Clarification for treatment of Bruder MaskUpdate to Section 2.2Topography added to Table 3	15 NOV 2018

[figure not shown]
SYNOPSIS

Protocol Title	MiBo ThermoFlo Lid Temperature Evaluation
Sponsor	JJVC, [name]
Clinical Phase	Phase 4
Trial Registration	This study will be registered on ClinicalTrials.gov by the Sponsor
Test Article(s)	Investigational Product: MiBo ThermoFlo Control Product: Bruder Moist Heat Single Eye Compress
Wear and Replacement Schedules	N/A
Objectives	
Determine anterior and posterior eyelid temperature after use of the MiBo ThermoFlo following standard clinical protocol and evaluate changes to the tear film with one MiBo ThermoFlo treatment session.
 
Primary Objective: Determine the temperature of the palpebral conjunctiva after MiBo ThermoFlo treatment and Bruder Mask (i.e. hot compress) treatment using the ICI-7320 infrared camera (Infrared Cameras Inc., Beaumont, TX)
 
Secondary Objectives: Tear Film Lipid Layer Thickness and Non-Invasive Tear Break Up Time post treatment

Study Endpoints	
Primary endpoint(s): Palpebral Conjunctival Temperature
 
Secondary endpoint(s): Tear Film Lipid Layer Thickness, Non-invasive tear break up time (NITBUT)

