2. STUDY OBJECTIVES, ENDPOINTS AND HYPOTHESES

2.1. Objectives

The primary study objective of this pilot study is to measure posterior eyelid temperature (palpebral conjunctiva) to determine the ability of the MiBo ThermoFlo to raise posterior eyelid temperature to levels sufficient to provide a therapeutic effect in the treatment of MGD.

Other observations in this study include testing whether the MiBo ThermoFlo treatment can induce a change in tear lipid layer thickness and/or non-invasive tear break up time after (1) 12-minute treatment session.

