2.2. Endpoints

The primary study endpoint is posterior eyelid temperature (palpebral conjunctiva) using the ICI-7320 infrared camera (Infrared Cameras Inc., Beaumont, TX). This metric has been selected as the ICI-7320 is FDA-approved [510(k) clearance] for use in medical imaging of any part of the body's surface. Collection of surface temperature with infrared video will allow for capture of the inner eyelid temperature while eyelids are inverted to access the palpebral conjunctiva. Other observations endpoints are Topography, Tear Lipid Layer thickness and Non-invasive Tear Break Up Time after treatment.

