14. STATISTICAL METHODS

14.1. General Considerations

Statistical Analysis will be undertaken by the sponsor or under the authority of the sponsor. A general description of the statistical methods to be implemented in this clinical trial is outlined below.

All data summaries and statistical analyses will be performed using the SAS software Version 9.4 (SAS Institute, Cary, NC). Throughout the analysis of data, the results for each subject/eye will be used when available for summarization and statistical analysis. Unscheduled visits will be summarized separately and will be excluded from the statistical analysis.

Summary tables (descriptive statistics and/or frequency tables) will be provided for all baseline variables, efficacy variables and safety variables as appropriate. Continuous variables will be

summarized with descriptive statistics (n, mean, standard deviation (SD), median, minimum and maximum). Frequency count and percentage of subjects or eyes within each category will be provided for categorical data.

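### Lipid layer thickness and break-up time are secondary endpoints with a promised test of change, but the plan gives them only generic descriptive tables

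*Combined protocol and SAP*

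**What the plan says.** **Objectives and endpoints.** The synopsis gives the secondary objectives as "Tear Film Lipid Layer Thickness and Non-Invasive Tear Break Up Time post treatment" and lists the same two measures as secondary endpoints. Section 2.1 places them among other observations, but with a firmer commitment: "testing whether the MiBo ThermoFlo treatment can induce a change in tear lipid layer thickness and/or non-invasive tear break up time". Section 2.2 states: "Other observations endpoints are Topography, Tear Lipid Layer thickness and Non-invasive Tear Break Up Time after treatment". Section 2.3 gives hypotheses about temperature only.

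**Data.** Section 7.2 measures LLT before treatment (step 1.10) and after it (1.19), and NITBUT before (1.11) and after (1.21), each in both eyes.

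**Analysis.** Section 14.5 describes one model, for eyelid temperature. Under "14.6. Secondary Analysis" the whole entry is N/A, and 14.7 on exploratory analyses is also N/A. Section 14.1 supplies the only text that reaches LLT and NITBUT: "Summary tables (descriptive statistics and/or frequency tables) will be provided for all baseline variables, efficacy variables and safety variables as appropriate". For continuous variables it names n, mean, SD, median, minimum and maximum. Section 14.4 puts all planned analyses under an overall 5% type I error rate. Section 14.10 says the analysis will follow the sections above it, with any change documented and justified in the study report.

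**The concern.** The plan sets a question and then states that there is no analysis for it. An entry of N/A under a heading reserved for secondary analysis is a positive statement, not an omitted detail. Given 14.10, any analysis of tear film change added later would be a departure to be explained.

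The choices left open are real ones. The LipiView work aid records average, minimum and maximum LLT, and warns that the maximum can reach a ceiling of 100+ nm. The Keratograph procedure records break-up over the whole cornea and names no summary value. The contrast is open too: change within the MiBo eye, or MiBo against Bruder. In an unmasked study analysed by or for the sponsor, making these choices after the data are seen would weaken a finding in either direction.

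**Working it through.** **1. Is there an analysis anywhere that meets the commitment in 2.1?**

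| Needed to assess change | Where it might be | Found? |
|---|---|---|
| Pre and post values, both eyes | 7.2, steps 1.10, 1.11, 1.19, 1.21 | Yes |
| Summary value for each measure | LipiView work aid; Keratograph SOP | Several for LLT; none named for NITBUT |
| Hypothesis | 2.3 | No, temperature only |
| Contrast and model | 14.5, 14.6, 14.7 | No |
| Descriptive tables | 14.1 | Yes, in general terms |
| Change from baseline | 14.1 | Not mentioned |
| Interval or test | 14.5 | Temperature only |
| Place in the 5% error rate | 14.4 | Not stated |

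**2. What can the 14.1 tables deliver?** Suppose they are split by treatment and time point, which 14.1 does not specify, and the same subjects contribute to both columns. Then mean(post) − mean(pre) = mean(post − pre), so a reader can recover the average change. Its precision cannot be recovered: Var(change) = Var(pre) + Var(post) − 2 Cov(pre, post), and the covariance is not among the listed statistics. The tables would show the size of a change but not its uncertainty.

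**3. Would an analysis be worth having at this sample size?** The plan gives no SD or effect size for LLT or NITBUT and no formal sample size calculation (14.2), so there is no stated figure to reproduce. In units of the SD of the within-subject change, with simple paired t methods and n = 12 (minimum completers) or n = 20 (target enrolment):

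- 95% half-width = t(0.975, n − 1) / √n. For n = 12: 2.201 / 3.464 = 0.64 SD. For n = 20: 2.093 / 4.472 = 0.47 SD.
- Change detectable with 80% power at two-sided 0.05 (noncentral t): 0.89 SD at n = 12 and 0.66 SD at n = 20.

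Only fairly large changes would be distinguishable from none, but the estimate would be informative for a pilot.

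**4. Error rate.** If both tear film endpoints were tested at 0.05 and were independent (an assumption), the chance of at least one false positive is 1 − 0.95² = 0.0975. Adding one temperature comparison gives 1 − 0.95³ = 0.1426. Splitting 0.025 + 0.025 keeps the two tear film endpoints at 0.05 but leaves nothing for temperature. Section 14.4 therefore needs a statement either way.

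**5. Which contrast answers 2.1?** Section 2.1 asks about change after MiBo, so the direct contrast is post minus pre in the MiBo eye. The between-eye contrast has a further problem. Randomization assigns treatment to eye, not order: MiBo is always step 1.15 and the 10-minute Bruder treatment always step 1.17, and LLT and NITBUT are measured only after both. The MiBo eye is therefore always measured at least 10 minutes later relative to its own treatment, while Section 1.5 describes the expected tear film effects as transient. Randomizing the eye does not remove this difference.

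**The case against.** The strongest reply has three parts.

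First, this is a self-described pilot without a formal sample size, and descriptive reporting of non-primary endpoints in 12 to 20 subjects is defensible. The synopsis objective asks only for post-treatment values, which 14.1 would supply; the word testing occurs only in 2.1, under other observations. This is fair as far as it goes, and it exposes an inconsistency in status between the synopsis and 2.1–2.2. It does not remove the gap: even as other observations, the measures carry a promised test, and 14.7 is as empty as 14.6. Declaring the endpoints descriptive and rewording 2.1 and the synopsis would make the document consistent, but would leave an answerable question without an estimate of precision.

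Second, a reader might infer that the secondary objective cannot be answered at all. The documents do not support that. The data are collected in both eyes at both times, and 14.1 commits to tables for all efficacy variables; its phrase about what is appropriate does not exclude change scores. What is missing is the specification.

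Third, a reader might try to size the problem as precision lost by ignoring the pairing of eyes or of visit time points. No unpaired comparison is planned and no correlation is given, so no such figure can be attached to this plan.

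**Conclusion.** The gap is confirmed from the text: followed as written, the plan produces generic summaries of LLT and NITBUT and never the assessment of change that 2.1 commits to. It is a gap in prespecification, not in data, and it does not touch the primary endpoint. It should be corrected before the database is locked.

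The precision figures assume approximately normal changes and complete pairs, and are in SD units because the plan supplies no SD. Two limits remain after correction. The within-MiBo-eye change is an uncontrolled before-and-after contrast, taken after a delay that includes the Bruder treatment. The comparison with Bruder is confounded with time since treatment.

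**What to change.** - **14.6:** replace N/A with an analysis of change (post minus pre) in average LLT and in one named NITBUT summary value. For each, fit a mixed model with treatment and mean-centred, eye-specific baseline as fixed effects and subject as a random effect. Using change as the outcome with a centred baseline lets the model give the mean change in the MiBo eye directly.
- **Contrasts:** report the within-MiBo-eye mean change with a two-sided 95% confidence interval as the answer to 2.1. Report MiBo minus Bruder as supportive only, with the caveat on treatment order and time since treatment beside it.
- **14.4:** state whether these intervals fall inside the overall 5% error rate. If outside, amend the sentence that now covers all planned analyses; if inside, give the allocation rule.
- **Synopsis and 2.1–2.2:** give the two endpoints one status throughout.

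The cost is a short paragraph in 14.6, one model per endpoint, a sentence in 14.4 and a wording change in the objectives. No new measurements are required.

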14.7. Other Exploratory Analyses

N/A.

14.8. Interim Analysis

There will not be an interim analysis performed on this study.

14.9. Procedure for Handling Missing Data and Drop-Outs

Missing or spurious values will not be imputed. The count of missing values will be included in the summary tables and listings.

14.10. Procedure for Reporting Deviations from Statistical Plan

The analysis will be conducted according to that specified in above sections. There are no known reasons for which it is planned to deviate from these analysis methods. If for any reason a change is made, the change will be documented in the study report along with a justification for the change.

15. DATA HANDLING AND RECORD KEEPING/ARCHIVING

15.1. Electronic Case Report Form/Data Collection

The data for this study will be captured on electronic case report forms (eCRFs) using an EDC system (Bioclinica). An authorized data originator will enter study data into the eCRFs using the EDC system. Data collected on equipment that is not captured in EDC will be formatted to the specification of the JJVC database manager and sent to JJVC for analysis. In the event that data is collected using paper Case Report Forms, double data entry will be utilized to prevent data entry error.

The clinical data will be recorded on dedicated eCRFs specifically designed to match the study procedures for each visit. Once completed, the eCRFs will be reviewed for accuracy and completeness and signed by the Investigator. The sponsor or sponsor's representatives will be authorized to gain access to the subject recordation for the purposes of monitoring and auditing the study.

Edit checks, electronic queries, and audit trails are built into the system to ensure accurate and complete data collection. Data will be transmitted from the clinical site to a secure central database as forms are completed or updated, ensuring information accuracy, security, and confidentiality. After the final database lock, the Investigator will be provided with Individual Patient Profiles (IPP) including the full audit trail on electronic media in PDF format for all of

the study data. The IPP must be retained in the study files as a certified copy of the source data for the study.

The content and structure of the eCRFs are compliant with ISO14155:2011.¹

15.2. Subject Record

At a minimum, subject record should be available for the following:

- subject identification
- eligibility
- study identification
- study discussion
- provision of and date of informed consent
- visit dates
- results of safety and efficacy parameters as required by the protocol
- a record of all adverse events
- follow-up of adverse events
- medical history and concomitant medication
- study supplies receipt/dispensing/return records
- date of study completion
- reason for early discontinuation of subject or withdrawal from the study, if applicable

The subject record is the eCRF or an external record. The author of an entry in the subject record must be identifiable. The first point of entry is the source record.

Adverse event notes must be reviewed and initialed by the Investigator.

16. DATA MANAGEMENT

16.1. Access to Source Data/Document

The Investigator/Institution will permit trial-related monitoring, audits, IEC/IRB review and regulatory inspection(s) by providing direct access to source data/documents. Should the clinical site be contacted for an audit by an IEC/IRB or regulatory authority, JJVC must be contacted and notified in writing within 24 hours.

16.2. Confidentiality of Information

Information concerning the investigational product and patent application processes, scientific data or other pertinent information is confidential and remains the property of JJVC. The Investigator may use this information for the purposes of the study only. It is understood by the Investigator that JJVC will use information developed in this clinical study about the development of the investigational product and therefore may disclose it as required to other clinical investigators and to regulatory agencies. To allow the use of the information derived from this clinical study, the Investigator understands that he/she has an obligation to provide complete test results and all data developed during this study to the Sponsor.

16.3. Data Quality Assurance

Steps will be taken to ensure the accuracy and reliability of data, include the selection of qualified investigators and appropriate clinical sites and review of protocol procedures with the Principal Investigator. The Principal Investigator, in turn, must ensure that all Sub-Investigators and clinical site personnel are familiar with the protocol and all study-specific procedures and have appropriate knowledge of the study article.

Training on case report form completion will be provided to clinical site personnel before the start of the study. The Sponsor will review case report forms for accuracy and completeness remotely during the conduct of the study, during monitoring visits, and after transmission to data management. Any data discrepancies will be resolved with the Investigator or designee, as appropriate.

Quality Assurance representatives from JJVC may visit clinical sites to review data produced during the study and to assess compliance with applicable regulations pertaining to the conduct of clinical trials. The clinical sites will provide direct access to study-related source data/documents and reports for monitoring and auditing by JJVC and for inspection by local and regulatory authorities.

17. MONITORING

The study monitors will maintain close contact with the Principal Investigator and the Investigator's designated clinical site personnel. The monitor's responsibilities will include:

- Ensuring that the investigation is being conducted according to the protocol, any subsequent amendments, and regulatory requirements are maintained
- Ensuring the rights and wellbeing of subjects are protected
- Ensuring adequate resources, including facilities, laboratories, equipment, and qualified clinical site personnel
- Ensuring that protocol deviations are documented with corrective action plans, as applicable
- Ensuring that the clinical site has sufficient test article and supplies
- Clarifying questions regarding the study
- Resolving study issues or problems that may arise
- Reviewing of study records and source documentation verification in accordance with the monitoring plan

18. ETHICAL AND REGULATORY ASPECTS

18.1. Study-Specific Design Considerations

Potential subjects will be fully informed of the risks and requirements of the study and, during the study, subjects will be given any new information that may affect their decision to continue participation. Subjects will be told that their consent to participate in the study is voluntary and may be withdrawn at any time with no reason given and without penalty or loss of benefits to which they would otherwise be entitled. Only subjects who are fully able to understand the

risks, benefits, and potential adverse events of the study, and provide their consent voluntarily will be enrolled.

18.2. Investigator Responsibility

The Principal Investigator is responsible for ensuring that the clinical study is performed in accordance with the signed agreement, the investigational plan, Section 4 of the ICH E6 guidelines on Good Clinical Practice (GCP),² and applicable regulatory requirements. GCP is an international ethical and scientific quality standard for designing, conducting, recording, and reporting studies that involve the participation of human subjects. Compliance with this standard provides public assurance that the rights, safety, and well-being of study subjects are protected, consistent with the principles of the Declaration of Helsinki 64th WMA General Assembly 2013³ and that the clinical study data are credible. The Investigator must maintain clinical study files in accordance with Section 8 of the ICH E6 guidelines on Good Clinical Practice (GCP),² and applicable regulatory requirements.

18.3. Independent Ethics Committee or Institutional Review Board (IEC/IRB)

Before the start of the study, the Investigator (or Sponsor when applicable) will provide the IEC/IRB with current and complete copies of the following documents (where applicable):

- Final protocol and, if applicable, amendments
- Sponsor-approved informed consent form (and any other written materials to be provided to the subjects)
- Investigator's Brochure (or equivalent information) and amendments
- Sponsor-approved subject recruitment materials
- Information on compensation for study-related injuries or payment to subjects for participation in the study
- Investigator's curriculum vitae, clinical licenses, or equivalent information (unless not required, as documented by IEC/IRB)
- Information regarding funding, name of the Sponsor, institutional affiliations, other potential conflicts of interest, and incentives for subjects
- Any other documents that the IEC/IRB requests to fulfill its obligation

This study will be undertaken only after IEC/IRB has given full approval of the final protocol, amendments (if any), the informed consent form, applicable recruiting materials, and subject compensation programs, and the Sponsor has received a copy of this approval. This approval letter must be dated and must clearly identify the documents being approved.

During the study, the Investigator (or Sponsor when applicable) will send the following documents to the IEC/IRB for their review and approval, where appropriate:

- Protocol amendments
- Revision(s) to informed consent form and any other written materials to be provided to subjects
- If applicable, new or revised subject recruitment materials approved by the Sponsor
- Revisions to compensation for study-related injuries or payment to subjects for participation in the study
- Investigator's Brochure amendments or new edition(s)

- Summaries of the status of the study (at least annually or at intervals stipulated in guidelines of the IEC/IRB)
- Reports of adverse events that are serious, unanticipated, and associated with the test articles, according to the IRB's requirements
- New information that may adversely affect the safety of the subjects or the conduct of the study
- Major protocol deviations as required by the IEC/IRB
- Report of deaths of subjects under the Investigator's care
- Notification if a new Investigator is responsible for the study at the clinical site
- Any other requirements of the IEC/IRB

For protocol amendments that increase subject risk, the amendment and applicable informed consent form revisions must be submitted promptly to the IEC/IRB for review and approval before implementation of the change(s).

At least once a year, the IEC/IRB will review and reapprove this clinical study. This request should be documented in writing.

At the end of the study, the Investigator (or Sponsor where required) will notify the IEC/IRB about the study completion. Documentation of this notification must be retained at the clinical site and a copy provided to the CRO or Sponsor as applicable.

